3.2 Secondary Objectives and Endpoints

For the secondary objectives, we will compare treatment and control arms based on the following list of clinical endpoints which capture different aspects of disease severity.

OBJECTIVES	ENDPOINTS (OUTCOME MEASURES)

1. Evaluate the clinical efficacy of convalescent plasma administration by comparing treatment vs control arms
 
 • Clinical Severity 
 ○ Ordinal scale: 
 ■ Time to recovery, defined by time to levels 1-3 on the ordinal scale ■ Time to an improvement of one category and two categories from Day 1 using an ordinal scale. ■ Participant clinical status using ordinal scale at Days 3, 5, 8, 11, 15, 22, and 29. ■ Mean change in the ordinal scale from Day 1 to Days 3, 5, 8, 11, 15, 22, and 29. 	
 • Clinical outcome assessed using ordinal scale daily while hospitalized and on Day 15, 22, and 29. • Clinical status assessment (8-point ordinal scale) includes: 
 1. Not hospitalized, no limitations on activities. 2. Not hospitalized, limitation on activities and/or requiring home oxygen; 3. Hospitalized, not requiring supplemental oxygen - no longer requires ongoing medical care; 4. Hospitalized, not requiring supplemental oxygen - requiring ongoing medical care (COVID-19 related or otherwise); 5. Hospitalized, requiring supplemental oxygen; 6. Hospitalized, on non-invasive ventilation or high flow oxygen devices; 7. Hospitalized, on invasive mechanical ventilation or ECMO; 8. Death

 ○ National Early Warning Score (NEWS): 
 ■ Time to discharge or to a NEWS of ≤ 2 and maintained for 24 hours, whichever occurs first ■ Change from Day 1 to Days 3, 5, 8, 11, 15, and 29 in NEWS. 	
 • NEWS assessed daily while hospitalized and on Days 15 and 29.

 ○ Oxygenation: 
 ■ Oxygenation free days to Day 29. ■ Incidence and duration of new oxygen use during the study. 	
 ■ Days of supplemental oxygen (if applicable)

OBJECTIVES	ENDPOINTS (OUTCOME MEASURES)

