8.1.2 Measures of clinical support, limitations and infection control

On each study day while hospitalized through Study Day 29, the following measures for the previous day will be recorded. i.e., on Day 3, Day 2 measures are assessed as occurring anytime in that 24 hour period (00:00 to 23:59h):

- Hospitalization
- Oxygen requirement
- Non-invasive mechanical ventilation (via mask) requirement

- High flow oxygen requirement.
- Invasive mechanical ventilation (via endotracheal tube or tracheostomy tube) requirement.
- ECMO requirement.
- Ongoing medical care preventing hospital discharge (COVID-19 related or other medical conditions)
- Limitations of physical activity (self-assessed).
- Isolated for infection control purpose

If drawn for clinical care, record inflammatory markers, including:

- Ferritin, C Reactive Protein, D-Dimer, Fibrinogen, Erythrocyte Sedimentation Rate, Triglycerides, IL-6.

If and when a participant is discharged from the hospital, they will continue with study visits as an outpatient, for all Study Days that are applicable, including Days 15, 29, and 60. Outpatient visits will involve the participant returning to clinic, unless other reasonable accommodations for evaluations and blood draws can be arranged. Day 22 Study visit can be as a phone call. Given the COVID-19 restrictions and the difficulty some of the participants might have to attend an in person visit after hospital discharge, the collection of Day 60 data for primary and secondary endpoints and the collection of Day 60 samples for exploratory tests may be performed up to 90 days following the Day 60 visit. For these participants, the Day 60 data may be obtained from the information already entered in the clinical records by any clinician, or by contacting the participant by phone up to 90 days following the Day 60 visit to obtain retrospective data.

8.1.3 *Ordinal Scale*

The ordinal scale is an assessment of the clinical status at the first assessment of a given study day. From the measures collected in 8.1.2.1, this ordinal scale can be constructed.

The scale used in this study is as follows:

1. Not hospitalized, no limitations on activities.
2. Not hospitalized, limitation on activities and/or requiring home oxygen;
3. Hospitalized, not requiring supplemental oxygen - no longer requires ongoing medical care;
4. Hospitalized, not requiring supplemental oxygen - requiring ongoing medical care (COVID-19 related or otherwise);

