9.4 Statistical Analyses

9.4.1 General Approach

Descriptive statistics (mean, standard deviation, minimum, median interquartile range, and maximum values for continuous variables; and frequencies and percentages for categorical variables) will be computed for all study variables for the above populations. Unless otherwise specified, a complete case analysis will be considered such that missing values will not be replaced, and calculations will be done on available reported values. If there is a substantial amount of missing data we may consider imputation methods and adjust the analyses accordingly. Analyses will primarily be descriptive; estimates will be presented with 95% confidence intervals. Any significance testing will be done at the 0.05 level. Details for the primary and key secondary analyses are provided below. A formal Statistical Analysis Plan (SAP) will be developed prior to performing analyses of the study endpoints.

9.4.2 *Analysis of the Primary Endpoint(s)*

The primary safety endpoint is cumulative incidence of serious adverse events (SAEs) at Day 29, calculated separately by arm as the percent of individuals who had at least one SAE by Day 29. The SAE rate at all other time points of the study will also be calculated. The overall SAE incidence will be presented, as well as separately by system organ class and preferred term groupings. Percentages will be based on the number of participants who were treated (the safety analysis set). Additional frequencies will be presented with respect to maximum severity and to relationship to COVID19 and study product. Multiple occurrences of the same AE will be counted only once according to the highest occurring grade and relationship to study product/COVID19.

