Cumulative incidence curves will be considered for time-to-event endpoints, treating death as a competing risk. Gray's test, or if the cause-specific hazard ratio was of interest the log-rank test, will be used to compare groups. Binary proportions will be estimated along with Clopper-Pearson 95% confidence intervals and compared between arms using Fisher's exact test. Continuous endpoints will be summarized with means, SD and normal 95% confidence intervals; Wilcoxon rank-sum will be used to compare arms for continuous endpoints. Ordinal endpoints (e.g. 8-point clinical severity score) will be summarized by their multinomial proportions across the different categories at Study Day 15,

22 and 29. An exact Mann-Whitney test will be used to test for whether the ordinal clinical severity was higher in one arm versus the other for ordinal endpoints. Further details for the analysis of secondary endpoints will be provided in the Statistical Analysis Plan.

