12 APPENDIX

12.1 Schedule of Activities (SoA)

The following page outlines all of the assessments to be conducted during the study. A detailed presentation of assessments immediately follows the table.

Table 4: Schedule of Activities

	Screen	Baseline	Study Period				
	While inpatient			While inpatient or as outpatient visits			
Day +/- Window	-1 or 1	1	Day 2 to 29	15 ⁷ ± 2	22 ⁷ ± 3	29 ⁷ ± 3	60 ⁷ ± 5 ¹⁰
ELIGIBILITY							
Informed consent	X						
Demographics & Medical History	X						
Targeted physical exam	X						
Review SARS-CoV-2 results	X						
STUDY INTERVENTION							
Randomization		X					
Administration of investigational plasma		X					
STUDY PROCEDURES							
Vital signs including SpO ₂		X ⁴	Daily until discharge or Day 29 of hospitalization	X		X	X
Clinical data collection ¹		X ⁴	Daily until discharge or Day 29 of hospitalization	X	X ⁸	X	X
Targeted medication review		X ⁴	Daily until discharge or Day 29 of hospitalization	X		X	X
Adverse event evaluation		X ⁴	Daily until discharge or Day 29 of hospitalization	X	X	X	X
SAFETY LABORATORY							
Type and Screen	X ^{2,3}						
Safety hematology, chemistry and liver tests		X ^{4,5,6}	Day 3, 5, 8, 11 (all ± 1 day) if hospitalized ^{5,6}	X ⁹		X ⁹	
Pregnancy test for females of childbearing potential	X ^{2,3}						
RESEARCH LABORATORY							
Oropharyngeal swab or endotracheal sample		X ⁵	Day 3, 5, 8, 11 (all ± 1 day) if hospitalized	X			

Blood for research		X ⁵	Day 3, 8, (all ± 1 day)	X		X	X
--------------------	--	----------------	-------------------------	---	--	---	---

1 Refer to [Section 8.1](#) of the protocol for details of clinical data to be collected including ordinal score, NEWS, oxygen requirement, mechanical ventilator requirement, etc.

2 Screening laboratory tests include: ALT, AST, creatinine (and calculate an estimated glomerular filtration rate (eGFR)), and pregnancy test.

3 Laboratory tests performed in the 48 hours prior to enrollment will be accepted

4 Baseline assessments should be performed prior to study drug administration. Laboratory tests performed as part of routine clinical care in the 24 hours prior to first dose will be accepted for the baseline safety laboratory tests. Baseline may be the same as the screening laboratory tests.

5 Safety laboratory tests include WBC with differential, hemoglobin, platelets, creatinine, glucose, total bilirubin, ALT, AST, and PT.

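### Secondary ordinal endpoints at Days 3, 5, 8 and 11 have no scoring rule for participants already discharged, and the complete-case default would omit these best outcomes

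*Combined protocol and SAP*

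**What the plan says.** **Endpoint days.** Protocol 3.2 lists "Participant clinical status using ordinal scale at Days 3, 5, 8, 11, 15, 22, and 29" and "Mean change in the ordinal scale from Day 1 to Days 3, 5, 8, 11, 15, 22, and 29". The exploratory list in 3.3 repeats both.

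**Collection.** The outcome-measures column of 3.2 says "Clinical outcome assessed using ordinal scale daily while hospitalized and on Day 15, 22, and 29". Table 4 (12.1) sets clinical data collection for Days 2 to 29 as "Daily until discharge or Day 29 of hospitalization", with later contacts at Days 15, 22, 29 and 60. Section 8.1.2 has the same limit for the components of the scale: "On each study day while hospitalized through Study Day 29, the following measures for the previous day will be recorded".

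**Scale.** A survivor outside hospital is level 1 or level 2. Level 2 is "Not hospitalized, limitation on activities and/or requiring home oxygen". Death is level 8. Days of hospitalisation and date of death are outcome measures in 3.2.

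**Analysis.** In 9.4.1 the default, unless otherwise specified, is complete case: "missing values will not be replaced, and calculations will be done on available reported values". Imputation may be considered if much is missing, with no method or trigger given. In 9.4.3 ordinal endpoints "will be summarized by their multinomial proportions across the different categories at Study Day 15", 22 and 29, and are compared with an exact Mann-Whitney test. Section 9.2 says efficacy follows intent-to-treat with outcomes on all enrolled participants. It expects very little missing early data because patients are in hospital at enrolment. Further detail is left to a formal SAP that is not in the text reviewed.

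**The concern.** A participant who goes home before Day 3, 5, 8 or 11 has no scheduled ordinal assessment on that day, and no section says what level to assign. If the 9.4.1 default is applied, that participant leaves the comparison because of a good outcome after randomisation. Deaths stay in, since death is a scale level with a recorded date.

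If plasma speeds discharge, more successes are removed from the plasma arm than from control, and the arms are compared on those still ill or dead. Mean change loses its largest improvements: from the eligible baseline levels 5 to 7, discharge to level 1 or 2 is a fall of 3 (5 − 2) to 6 (7 − 1) categories. The expectation of low early missingness in 9.2 does not allow for early discharge.

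**Working it through.** **1. The plan's own figure.** The plan gives no power for ordinal status at Days 3 to 11. The nearest figure is about 80% for 0.50 vs 0.80 with 40 per arm (9.2). Pearson, two-sided 0.05, pooled proportion 0.65: z = [0.30·√40 − 1.96·√(2·0.65·0.35)] / √(0.25 + 0.16) = (1.897 − 1.322)/0.640 = 0.90, so power is 0.816. This reproduces, and the same n and alpha are used below.

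**2. Worked example.** Assumed Day 8 counts, 40 per arm, with the extra plasma discharges drawn from levels 4 and 5:

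| | Discharged | L4 | L5 | L6 | L7 | Death |
|---|---|---|---|---|---|---|
| Control | 10 | 5 | 11 | 5 | 7 | 2 |
| Plasma | 20 | 2 | 4 | 5 | 7 | 2 |

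- *Everyone scored, discharged = 2.* Control (20+20+55+30+49+16)/40 = 190/40 = 4.75. Plasma (40+8+20+30+49+16)/40 = 163/40 = 4.075. The difference is −0.675 (favours plasma). P(plasma better, ties counted half) = 931/1600 = 0.58.
- *Discharged dropped, deaths kept.* Control 170/30 = 5.67. Plasma 123/20 = 6.15. The difference is +0.48 (favours control). P(plasma better) = 231/600 = 0.385.
- *Deaths dropped as well.* 154/28 = 5.50 vs 107/18 = 5.94, a difference of +0.44. The reversal does not depend on how deaths are handled.
- *Unknown split between levels 1 and 2.* Worst case for plasma (plasma all 2, control all 1): 4.075 − 4.50 = −0.43. Best case: 3.575 − 4.75 = −1.18. The sign holds throughout, and the rank test is the same whether all discharged are coded 1 or all coded 2.

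If the extra discharges (10 vs 16) come about evenly from all levels, the difference is 4.20 − 4.75 = −0.55 with everyone scored. With discharged dropped it is (168 − 32)/24 − 170/30 = 5.67 − 5.67 = 0.00, so the benefit is hidden.

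These are mean levels. They carry over to mean change only where the Day 1 means of those compared are equal, which is not modelled here.

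**3. Range.** Simulation, 40 per arm, 10–40% of controls discharged and 10–25 points more on plasma (all assumed):
- Gain from levels 4 and 5: the mean difference is −0.27 to −0.68 with everyone scored and +0.12 to +0.69 with discharged dropped. Plasma looks worse in 66–96% of trials, against 6–26% with everyone scored.
- Gain from all levels in proportion: −0.36 to −0.92 becomes about 0.00, and power in the right direction falls from 11–57% to 2–3%.

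**4. By study day.** The documents give no discharge rate by day. As a rough guide, the SARS plasma series in 2.2.2 had 33 of 80 meeting discharge criteria within 22 days. With a constant hazard (assumption) the proportion by d days is 1 − (1 − 0.4125)^(d/22). Taking d as elapsed days from Day 1, or as the study day itself: Day 3, 4.7–7.0%; Day 5, 9.2–11.4%; Day 8, 15.6–17.6%; Day 11, 21.5–23.4%.

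Power of a two-sided Mann-Whitney test (normal approximation) for a common odds ratio of 2.5, under assumed in-hospital mixes:

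| Control discharged | Everyone scored | Discharged dropped |
|---|---|---|
| 6% (about Day 3) | 61% | 48% |
| 10% (about Day 5) | 63% | 39% |
| 23% (about Day 11) | 62% | 21% |

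A repeat with the in-hospital control mix of step 2 (5/11/5/7/2 of 30; 4,000 trials per row) gives 61% to 47%, 61% to 40% and 62% to 23%.

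**The case against.** The strongest reply is that the value is not really missing. Section 8.1.3 builds the scale from recorded measures, hospitalisation is one of them, and a discharged survivor is level 1 or 2 by definition. A reader might infer from the schedule that discharged participants cannot be scored. The documents do not support that: only the split between levels 1 and 2 is unknown. It follows that the two columns of 3.2 can be read together, and the plain mismatch of days is between 3.2 and 9.4.3. What stands is that no section says the known level will be assigned.

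A reader might also infer that exclusion is settled. It is not. The 9.4.1 rule opens with an exception for anything otherwise specified and allows imputation, 9.2 points towards including everyone, and the separate SAP may contain a rule. But an option with no method or trigger, in an open-label trial, is weak protection, and the default that is written down leads to omission.

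The level mixes and the treatment effect are assumed, and the SARS series is an uncontrolled group from another disease. This limits the exact sizes; the direction held in every scenario tried.

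Finally, this is a phase 1 trial with mainly descriptive analyses, and time to recovery and duration of hospitalisation already capture faster discharge. That is fair and limits the weight of the point.

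**Conclusion.** The point holds for the secondary ordinal endpoints at Days 3, 5, 8 and 11, and for their exploratory copies in 3.3. The collection schedule and the complete-case default, followed as written, select on a post-randomisation outcome and conflict with the all-enrolled statement in 9.2.

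The size depends on the share discharged. It would be wrong to infer that every early time point loses most of its power: under the assumptions above the loss is about 13 points at 6% discharged (61 − 48), 24 at 10% (63 − 39) and 41 at 23% (62 − 21). Reversal of sign is possible if plasma mainly speeds discharge of milder patients, but it is not a general prediction. Nor does the gap reach the Day 29 primary score, time to recovery or survival. The change is worth making before analysis and does not threaten the trial's main conclusion.

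**What to change.** State in 3.2 and 9.4.3 that on Days 3, 5, 8 and 11:

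- a participant discharged alive and not known to be readmitted is scored in one tied best category (levels 1–2), kept separate from hospitalised level 3, whose level is recorded;
- a participant who has died is scored 8;
- the exact Mann-Whitney test includes all randomised participants.

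For mean change, assign a stated value (for example 2, with 1 as a sensitivity analysis) or rely on the ranked comparison. Reconcile the summary days in 9.4.3 (15, 22, 29) with those in 3.2.

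Cost: wording in the protocol and SAP, with no added visits, since days of hospitalisation and date of death are already collected. Small downsides: levels 1 and 2 are not separated on these days, and readmission before Day 15 has to be taken from hospitalisation records and later contacts. Table 4 names readmission explicitly only for the Day 22 call.

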5 STUDY POPULATION

5.1 Inclusion Criteria

1. Adult ≥ 18 years of age
2. Laboratory-confirmed SARS-CoV-2 infection as determined by PCR or other authorized or approved assay in any specimen collected within 72 hours prior to enrollment.

Note – An exception must be requested to the Sponsor if ≥ 72 hours since positive test.

3. Hospitalized in participating facility.
4. Documentation of pneumonia with radiographic evidence of infiltrates by imaging (e.g., chest x-ray or CT scan).
5. Abnormal respiratory status that is judged worse than baseline by the investigator and as documented at any point within 24 hours prior to randomization, consistent with ordinal scale levels 5, 6 or 7, specifically defined as:
 - Room air saturation of oxygen (SaO_2) $< 93\%$, OR
 - Requiring supplemental oxygen, OR
 - Tachypnea with respiratory rate ≥ 30
6. Patient or proxy is willing and able to provide written informed consent and comply with all protocol requirements

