6.3 Measures to Minimize Bias: Randomization and Blinding

Individuals will be randomized to the intervention or control arm in a 1:1 ratio. Randomization will occur in a blinded fashion using Redcap. Allocation will be determined using a permuted block algorithm with varying block sizes. We will stratify randomization based on whether or not a patient is on mechanical ventilation and on [remdesivir](#) at baseline. Though the intervention will not be blinded, we will attempt to minimize bias by blinding study personnel, such as individuals running laboratory assays, to the extent that it is possible.

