- The key parameter of interest will be the comparison of clinical severity between individuals receiving the experimental intervention versus control, as measured by a clinical severity score that takes into account the modified 8-point ordinal severity score in a prioritized manner. For the modification, recovery will be defined by reaching levels 1-3 on the 8-point ordinal severity score. The null hypothesis is that experimental individuals will have the same median severity as control individuals. The severity score is based on a procedure by Shaw and Fay 2016 [21], which ranks participants based on their Day 29 ordinal severity. All survivors better than non-survivors, individuals with shorter recovery times as better, and individuals with shorter times to death as worse. For individuals who survive but had not yet recovered by Day 29, they will be ranked according to their Day 29 ordinal severity, with individuals achieving the same ordinal severity being ranked according to time to reaching that level of severity. More details are provided in the Statistical Analysis Plan (SAP). This type of severity score, or prioritized outcome, has been advocated in many settings such as infectious disease and cardiovascular outcome settings [22,24,25]. This analysis will have more power to detect differences than looking only at one individual endpoint. Shaw and Fay 2016 showed this test statistic can be interpreted as a weighted average of the log-rank type test statistic for survival and the one for time to recovery amongst survivors. The individual endpoints, time to recovery and time to death, will also be examined as secondary endpoints.
- **Secondary Efficacy Endpoint(s):** Comparison between arms of time to recovery and survival.
- The null hypothesis is that the two arms will have the same recovery time and the same survival time. Kaplan-Meier survival curves will be calculated by arm and compared with a Peto-Peto generalized Wilcoxon test. In the event that deaths occur, the cumulative incidence of recovery will be estimated and compared between groups using Gray's test, which will be able to capture a lower time to recovery due to either a slower event rate or a higher death rate. For interpretive purposes the cause specific hazard ratios for will also be calculated for each event type,

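### Mean change on the 8-point scale counts a death from level 7 (+1) less than an intubation from level 5 (+2): a minor fault in one secondary endpoint

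*Combined protocol and SAP*

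**What the plan says.** Section 3.2 lists, as a between-arm secondary endpoint, "Mean change in the ordinal scale from Day 1 to Days 3, 5, 8, 11, 15, 22, and 29". The same item appears in the secondary and exploratory tables of the synopsis and in section 3.3.

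The relevant levels are 5, "Hospitalized, requiring supplemental oxygen"; 6, "Hospitalized, on non-invasive ventilation or high flow oxygen devices"; 7, "Hospitalized, on invasive mechanical ventilation or ECMO"; and 8, death. Section 5.1 admits participants whose respiratory status is "consistent with ordinal scale levels 5, 6 or 7". Section 6.3 says "We will stratify randomization based on whether or not a patient is on mechanical ventilation", so a mix of starting levels is planned.

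Section 9.4.3 does not name mean change. It gives two generic rules:
- Continuous endpoints get means, SDs and normal 95% confidence intervals, and "Wilcoxon rank-sum will be used to compare arms for continuous endpoints".
- Ordinal endpoints get category proportions and an exact Mann-Whitney test.

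For the primary efficacy score, section 9.1 sets an explicit order: "All survivors better than non-survivors, individuals with shorter recovery times as better, and individuals with shorter times to death as worse". The available text gives no such rule for the change score and no reason to treat the levels as equally spaced.

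**The concern.** A change score takes one step on the scale to mean the same everywhere. Here the step from 7 to 8 is the step from ventilated to dead, and it counts the same as the step from 5 to 6, from supplemental oxygen to high-flow or non-invasive support. Two participants who start at different levels can then be ordered in a way few readers would accept: one who was ventilated and died shows a smaller deterioration than one who was on oxygen, was intubated and lived.

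Section 2.3.3 describes the mortality risk as substantial, particularly in ventilated patients. That is the group in which a death adds only one point. If the endpoint is tested between arms at seven days, a comparison could lean towards the arm with more deaths.

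**Working it through.** The plan gives no sample size, power or expected value for this endpoint, so there is no stated figure to reproduce. The inputs are the level codes (section 3.2), the entry levels (section 5.1) and 40 per arm (section 9.2).

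**Step 1: change scores.** Change = level at visit − level on Day 1.

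| Day 1 level | to 6 | to 7 | to 8 (death) |
|---|---|---|---|
| 5 | +1 | +2 | +3 |
| 6 | 0 | +1 | +2 |
| 7 | −1 | 0 | +1 |

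Across rows, death from 7 (+1) is below intubation from 5 (+2). It equals the 5 to 6 step (+1) and intubation from 6 (+1). Within each row, death is the largest value.

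**Step 2: effect on the mean.** Assume 40 per arm, 20 starting at level 5 and 20 at level 7. This split is illustrative, because the documents give none. Arm A has 6 deaths from level 7. Arm B has 6 intubations from level 5 and no deaths. Everyone else is unchanged.

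- Arm A: 6 × 1 / 40 = +0.15
- Arm B: 6 × 2 / 40 = +0.30

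The arm with the six deaths has the better mean. With 10 deaths against 5 intubations the means are equal: 10 × 1 / 40 = 5 × 2 / 40 = 0.25.

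**Step 3: source of the effect on the mean.** Difference in mean change = difference in mean visit level − difference in mean Day 1 level. The two arms start alike here, so the last term is 0. Mean visit levels are 6.15 and 6.30, and their difference of 0.15 equals 0.30 − 0.15. Subtracting Day 1 has changed nothing, so the effect on the mean comes from equal spacing of the levels.

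**Step 4: effect on a rank-sum test of change.** There are 40 × 40 = 1,600 cross-arm pairs.

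- B worse: 6 intubations (+2) against all 40 in A = 240
- A worse: 6 deaths (+1) against the 34 unchanged in B = 204
- Tied: 34 × 34 = 1,156

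The ranks also lean towards the arm with the deaths. In 6 × 6 = 36 of those pairs a death is placed ahead of a survivor. If every death is ranked below every survivor, A is worse in 6 × 40 = 240 pairs and B in 6 × 34 = 204, so the lean reverses.

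**Step 5: the status comparison on the same data.** Arm A has 20 at level 5, 14 at 7 and 6 at 8. Arm B has 14 at 5 and 26 at 7.

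- A better: 20 × 26 = 520
- A worse: 14 × 14 + 6 × 40 = 436

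Every death ranks below every survivor here, yet the total still leans to A, because six more people in B have left level 5. The fault specific to the change score is therefore the 36 misordered pairs. The overall lean in one constructed example is not the test of it.

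**Step 6: size for a smaller effect.** Four deaths prevented among ventilated participants who stay at level 7 move the arm mean by 4 × 1 / 40 = 0.10 level. Two extra 5 to 7 intubations cancel that (2 × 2 / 40 = 0.10), as do four 5 to 6 steps (4 × 1 / 40 = 0.10). If the four survivors instead reached level 3, the shift would be 4 × 5 / 40 = 0.50.

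**The case against.** The strongest reply is that the trial does not depend on this endpoint. Clinical status at the same seven days is the adjacent item in section 3.2, with death as its worst level. Survival time and 14- and 28-day mortality are separate endpoints, survival is a key secondary endpoint in section 9.4.3, and section 9.4.1 calls the analyses primarily descriptive. A mortality effect would not be hidden. All of this stands, and it makes the point minor.

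The rank-sum test on change is also an inference from a generic sentence, and section 9.4.3 leaves further detail to a SAP whose separate text is not in the document. That stands too, so the statement about ranks is conditional.

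A reader might infer more than the documents support:

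- *That the endpoint treats death as the lesser harm in general.* It does not. From levels 5, 6 and 7, death scores +3, +2 and +1, always the largest change available.
- *That the limit set by the starting level causes the cancellation on the mean.* With balanced starting levels the same cancellation occurs in the raw mean score (Step 3).
- *That the plan contradicts its own principle.* The survivors-first order is stated for the primary score only. Section 3.2 says the secondary endpoints capture different aspects of severity.
- *That a few changes of oxygen device would cancel a mortality benefit.* The two-for-four trade uses intubations from level 5. Device steps from 5 to 6 offset deaths from level 7 only one for one.

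What remains is that no available text stops a between-arm test of change from ranking a ventilated participant's death ahead of a survivor's intubation.

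**Conclusion.** The point holds as a minor fault in one non-key secondary endpoint. Raw mean change assumes equal spacing and gives death no special value. Across starting levels, a death from level 7 counts half as much as an intubation from level 5. If the rule for continuous endpoints is applied without stratification, the rank-sum test orders those two outcomes the same way. The primary efficacy score, the ordinal status comparison and the mortality endpoints are not affected.

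The sizes shown (+0.15 against +0.30; 204 against 240 of 1,600 pairs; 0.10 to 0.50 level for four deaths prevented) rest on constructed arms. The documents give no expected mortality and no expected share of ventilated participants. The example also needs the arms to differ in opposite directions in the two strata.

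The point assumes mixed starting levels, as sections 5.1 and 6.3 imply. Section 4.1 describes the population as intubated and mechanically ventilated. If everyone started at level 7, the misordering could not occur. Those sections should be reconciled.

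**What to change.** In sections 3.2 and 9.4.3, and in the matching items of the synopsis and section 3.3:

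1. Do not use raw mean change for between-arm inference. Report it descriptively in all participants, with death coded 8 and the number of deaths by arm shown beside it at each day. Do not restrict it to survivors: that conditions on an outcome after randomisation, and the arms would no longer be comparable.
2. If change from Day 1 is tested, give every death the worst rank, below all survivors, and keep the full change scores among survivors. Use the rank-sum or exact Mann-Whitney test already planned. Collapsing change into a few categories is not needed and would lose information on recovery.
3. Otherwise rely on the ordinal status comparison at the same days. Section 9.4.3 names only Days 15, 22 and 29 for the category summaries, while section 3.2 lists seven days for status, so the text should say which days are compared.

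The cost is wording, with no new data. Mean change would no longer be a tested figure. Some dependence on the starting level remains among survivors, since a participant who starts at level 7 and lives cannot record a worsening.
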